6.8. Safety Analyses

All safety summaries and analyses will be based upon the safety population. Details of the analyses are described in the following sections.

6.8.1. Extent of Exposure

LY3405105 will be administered PO QD or 3 times a week (TIW [MWF or TTS]) on a 28-day cycle. Based on available human PK exposure data, the intermittent dosing schedule (Part A2) will no longer be pursued in the study.

The actual cumulative dose taken of LY3405105 will be derived from the difference between the total number of tablets/capsules dispensed and returned over the course of the patient's treatment taking into account the dose strengths (1 mg and 5 mg).

The duration of therapy for the QD schedule will be calculated as last dose date-first dose date+1. The duration of therapy for the TIW schedule will be calculated as last dose date-first dose date+(28/[4×3]).

A summary of exposure will be provided for each study drug, including cycle received, cumulative dose, and duration of therapy.

A summary of dose intensity will be provided for each study drug. Dose intensity (per day) is calculated as total actual dose taken/duration of therapy (day). Relative dose intensity is calculated as $100 \times (\text{actual dose intensity per day}/\text{planned dose intensity per day})$.

Note that planned dose is the same as actual dose if there is no dose modification or cycle delays.

A summary of dose adjustments will be provided for each study drug, including dose omissions, dose reductions, cycle delays, and the corresponding reasons for dose adjustment.

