ECG		X	X		X	X	X	X		
ECG collections that are underlined and in bold are mandatory. All other ECG collections are optional.
 
Baseline: Single ECG only
 
Cycle 1 Day 1: collect digital ECGs for QT analysis in triplicate at predose, 2 hrs postdose. If possible, a 24 hr reading should be taken.
 
Day 15: Predose (triplicate) A corresponding PK sample should be collected after the ECG reading.
 
Cycle 2: Single ECGs only (predose on D1 and D15)
 
Cycle 3-n: Single ECG on D1 (predose).
 
Perform additional evaluations in the setting of cardiac symptoms and/or at the discretion of the investigator. Perform locally.
	
Hematology*	X	X		X	X	X	X	X		≤ 3 days prior to start of each cycle, unless more frequent assessment is clinically indicated.	
Coagulation	X									Only collected at baseline, unless more frequent assessment is clinically indicated.	
Clinical chemistry*	X	X		X	X	X	X	X		≤ 3 days prior to start of cycle, unless more frequent assessment is	

Procedure	Baseline	All Remaining Parts on Treatment (Cycle = 28 days)						Post Treatment Follow-Up		Instructions	
	Days Prior to C1D1	Cycle 1 (± 3 Days)			Cycle 2 (± 3 Days)		Cycle 3-n (± 3 Days)	Short-Term ^a (30 ± 7 Days)	Long-Term (Every 90 ± 7 Days)		
		Day			Day		Day				
		≤ 28	1	8	15	1	15	1	Visit 801	Visit 802-8XX	
										clinically indicated.	
Urinalysis*	X	X			X		X	X		≤ 3 days prior to start of cycle, unless more frequent assessment is clinically indicated.	
Urine pregnancy test	X	X			X		X			Applies only to women of childbearing potential. Where required by local law or regulation, perform ≤ 3 day prior to start of every cycle prior to administration of study treatment.	
Patient diary		X		X						Provide patient diary Day 1. Completed daily by patient. Review at each study visit during Cycle 1.	
Survival assessment								X	X	Perform q 3 mo (± 7 days). If an in-person visit is not possible, confirm survival by contacting the patient directly via phone.	
LY3405105		X								Administer orally on Days 1-28 of a 28-day cycle. Patients should be advised to take dose after PK draw on days of PK collection.	

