7.2.1. Selection and Timing of Doses

The dosing cycle is defined as an interval of 28 days. During the monotherapy dose escalation, patients will receive doses once daily starting on Day 1 through Day 28 of a 28-day cycle. For visits where PK samples will be collected, patients are required to take the morning dose of LY3405105 at the hospital/clinic (not at home) after the predose PK sample collection has occurred.

LY3405105 will be administered on an empty stomach (meals should not be consumed within 1 hour either side of dosing). Doses should be taken approximately the same time each day (± 2 hours) as much as possible. If a patient misses or vomits a dose, that dose should be omitted. Patients must record the time and amount of each dose taken (or alternatively, the time and amount of the dose missed or vomited) in a daily diary.

A delay of a cycle due to holiday, weekend, bad weather, or other unforeseen circumstances will be permitted for a maximum of 7 days and not counted as a protocol deviation. The reason for interruption should be documented on the electronic case report form (eCRF).

A patient may continue to receive study treatment until confirmed progressive disease (Section 9.1), unacceptable toxicity, or discontinuation for any other reason (Section 8). Patients with documented progressive disease may be allowed to continue LY3405105 if the patient is tolerating treatment and, in the opinion of the investigator, is deriving clinical benefit from continuing study treatment and continuation of treatment is approved by the Sponsor.

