7.6. Treatment Compliance

Patient compliance with study drug will be assessed at each visit. LY3405105 compliance will be assessed by direct questioning, counting returned capsules/tablets/packages, and reviewing patient diaries. Deviations from the prescribed dosage regimen should be recorded on the CRF.

A patient will be considered significantly noncompliant if he/she misses more than 20% cumulative days of study medication (full doses) during each cycle. A patient may be considered significantly noncompliant if he or she is judged by the investigator to have intentionally or repeatedly taken more than the prescribed amount of medication.

7.6.1. **Evaluable Patients**

Patients who withdraw from the study before receiving study drug(s) will be replaced and will not be included in the safety or efficacy assessments. Safety analyses will be conducted on all patients who have received at least 1 dose of study drug, regardless of whether they are deemed evaluable for the assessment of a dose level.

Any patient who is discontinued from the study before receiving at least 80% of LY3405105 planned doses in Cycle 1 will be deemed non-evaluable for assessment of safety at that dose level and may be replaced unless they experience a DLT or dose omission/reduction due to toxicity prior to withdrawal. A patient may be deemed non-evaluable for assessment of a dose level in the event the patient experiences an AE which would meet DLT criteria, and furthermore has been determined through discussion between investigator and Lilly CRP/CRS to most likely be related to a concomitant medication or a prior line of immune therapy (in the case of immune-related AEs) due to previously established linkage.

If the patient is noncompliant during Cycle 1 due to reasons other than drug-related toxicity, he or she will be considered non-evaluable and may be replaced.

Non-evaluable patients may be replaced to ensure that at least 3 patients complete 1 cycle of therapy at each dose level, unless accrual to that dose level has stopped due to a DLT.

Patients who are not evaluable for PK, but who complete 1 cycle of therapy, may be replaced upon consultation with the investigator(s) and the Lilly CRP/CRS to ensure adequate PK data, unless accrual to that dose level has stopped due to a DLT.

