10.3.3.4. Extent of Exposure/Treatment Compliance

The number of cycles received, dose omissions, dose reductions, dose delays, and dose intensity will be summarized for all treated patients by treatment arm.

Study treatment compliance will be assessed as the proportion of treatment that is actually taken, relative to what is expected, after accounting for protocol-defined dose adjustments. Study treatment taken will be derived from the difference between the total number of pills dispensed and returned over the course of the patient's treatment.

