6.5. Treatment Compliance

Study treatment compliance will be assessed as the proportion of dose that is actually taken, relative to what is expected, after accounting for protocol-defined dose adjustments. The actual dose taken will be derived from the difference between the total number of tablets/capsules dispensed and returned over the course of the patient's treatment.

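### Dose taken is defined as pills dispensed minus returned, so unreturned supply and vomited doses push the descriptive compliance and dose-intensity figures upward

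*SAP*

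**What the plan says.** Three places define the amount taken, and they agree.

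- SAP 6.8.1, for cumulative dose: "The actual cumulative dose taken of LY3405105 will be derived from the difference between the total number of tablets/capsules dispensed and returned", converted to milligrams with the 1 mg and 5 mg strengths.
- SAP 6.5, for compliance: "The actual dose taken will be derived from the difference between the total number of tablets/capsules dispensed and returned".
- Protocol 10.3.3.4, also for compliance: "Study treatment taken will be derived from the difference between the total number of pills dispensed and returned".

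In SAP 6.8.1, dose intensity is this amount divided by the days on therapy, and relative dose intensity compares it with the planned daily intensity. The divisor comes from dates: "The duration of therapy for the QD schedule will be calculated as last dose date-first dose date+1". None of these sections says what happens to vomited doses or to supply that never comes back. SAP 6.2 adds no rule beyond not imputing missing data other than dates.

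The protocol collects more than the count. Section 7.2.1 says: "If a patient misses or vomits a dose, that dose should be omitted", and has the patient enter the time and amount of each missed or vomited dose in a diary. Section 7.6 says: "LY3405105 compliance will be assessed by direct questioning, counting returned capsules/tablets/packages, and reviewing patient diaries". It applies this at each visit and puts dosing deviations on the CRF. The Phase 1a Schedule of Activities (Table JZFA.2.1) says of the diary: "Completed daily by patient. Review at each study visit during Cycle 1". Table JZFA.2.2 has the same limit for Phase 1b.

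**The concern.** A pill count records what left the bottle. It cannot tell a retained dose from a vomited one, or a swallowed pill from one left at home. The numerator of dose intensity therefore includes every unreturned pill, while the divisor stops at the last dose. The two can cover different periods.

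At stake are the reported cumulative dose, compliance, dose intensity and relative dose intensity. Readers use these to judge whether the assigned dose was delivered. The setting makes the question relevant: the protocol's background section names gastrointestinal changes among the key nonclinical toxicities, and Section 7.1.1.1 exempts Grade 3 vomiting from DLT status if it lasts under 72 hours and is controlled. Vomiting could thus reduce delivery without registering as a DLT, and the pill count would not show the loss.

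A second, smaller matter is that scheduled diary review stops after Cycle 1, although Section 7.6 lists the diary among the sources for a compliance check at each visit.

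**Working it through.** The plan states no figure on this point, so there is none to reproduce. The check applies the SAP 6.8.1 formulas to simple cases.

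**Inputs from the documents**
- Cycle length of 28 days, once-daily dosing (Protocol 7.2.1).
- Dose taken = dispensed − returned (SAP 6.5 and 6.8.1, Protocol 10.3.3.4).
- Dose intensity = dose taken ÷ days from first to last dose, both days counted (SAP 6.8.1).
- Relative dose intensity (RDI) = 100 × actual ÷ planned intensity (SAP 6.8.1).

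**Assumptions, because the documents give no figures**
- 28 doses dispensed per cycle, at a constant dose, so planned intensity is 1 dose per day.
- The number of vomited doses and the stopping day are varied.

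**Case A: full cycle, *k* of 28 doses vomited, no supply left unaccounted for.** The SAP rule gives 28/28 = 100% whatever *k* is. Subtracting vomited doses gives 100 × (28 − *k*)/28:

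| *k* | SAP rule | Vomited doses subtracted |
|---|---|---|
| 1 | 100% | 96.4% |
| 3 | 100% | 89.3% |
| 5 | 100% | 82.1% |
| 6 | 100% | 78.6% |
| 10 | 100% | 64.3% |

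Each vomited dose accounts for 1/28 = 3.6 percentage points. Six is the first whole number above 20% of 28 days (5.6), the share of missed days that Section 7.6 uses for significant noncompliance. Section 7.6 does not say whether a vomited dose counts as missed.

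**Case B: last dose on Day *s* of Cycle 1, all doses taken to then, supply not returned.** True RDI is 100%. The rule gives 100 × 28/*s*:

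| Last dose | RDI by the SAP rule |
|---|---|
| Day 7 | 400% |
| Day 10 | 280% |
| Day 14 | 200% |
| Day 21 | 133% |
| Day 27 | 104% |

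**Case C: *c* full cycles, then a last dose on Day 10 of the next, with only that cycle's supply unreturned.** The rule gives 100 × (28*c* + 28)/(28*c* + 10):

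| *c* | Doses/days | RDI by the SAP rule |
|---|---|---|
| 1 | 56/38 | 147% |
| 2 | 84/66 | 127% |
| 3 | 112/94 | 119% |
| 6 | 196/178 | 110% |

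The effect fades as treatment lengthens.

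**Case D: both together.** Last dose on study Day 40, four doses vomited, Cycle 2 supply unreturned. The rule gives 56/40 = 140%. With vomited doses subtracted, the figure is 36/40 = 90%.

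**The case against.** Much of the case on the other side stands.

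- *A reader might infer that the diary and CRF dosing data are thrown away.* They are not. SAP 6.8.1 and Protocol 10.3.3.4 also summarise dose omissions, the SAP with reasons, and vomited doses may appear there. But nothing says they are entered as omissions, or that omissions correct the pill-count figures.
- *A reader might infer that the RP2D or the efficacy result is biased.* The documents do not support this. Protocol 10.3.2 rests the RP2D on DLTs, TEAEs, PK and PD. Section 7.1.1.2 rests escalation on the model recommendation and the observed DLT rate, with PK and PD. ORR uses all treated patients regardless of compliance, and plasma PK measures drug exposure directly.
- *A reader might infer that the overstatement is shown to be greatest with gastrointestinal toxicity, after abrupt discontinuation, or at sites that recover few bottles.* The formula points that way, but no vomiting or non-return rate is given.
- *The omission rule in Protocol 7.2.1 may mean only that the dose is not repeated.* That is a fair reading, and the rule then does not define dose taken. A vomited dose may also be partly absorbed, so subtracting it in full gives a lower bound.
- *The SAP does not expressly say that lost bottles count as taken.* True, but a return of zero gives that result. If the return is instead treated as missing, SAP 6.2 leaves the patient without a value. Either way a rule is needed.
- *SAP 6.8.1 notes that planned and actual dose coincide when nothing was modified or delayed.* Read as an expectation, the note is contradicted by Case B. Read as a rule, it could hold RDI at 100%, but cumulative dose would still be 28 doses for 10 taken.
- *An RDI of 280% would be noticed in data review.* Probably, but 104% or 110% might not be, and the vomiting error never exceeds 100%.
- *A diary is self-reported and may be missing for the patients who leave abruptly.* This is a good reason not to replace the pill count with the diary.

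**Conclusion.** The point holds for the descriptive exposure figures. The numerators of cumulative dose, compliance and dose intensity rest on pill counts alone, with no rule for vomited doses or unreturned supply, and the dose-intensity divisor ends at the last dose. Both gaps bias upward, and RDI can exceed 100% with no extra dose taken.

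The figures in the working are illustrations that depend on 28 doses being dispensed per cycle. The documents give no dispensing quantity, vomiting frequency or non-return rate, so the size in this trial cannot be computed. The consequence is confined to exposure and compliance reporting.

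The mismatch between diary review in Cycle 1 only and compliance assessment at each visit is real but minor, since questioning and pill counts continue after Cycle 1.

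**What to change.** In SAP 6.5 and 6.8.1 and Protocol 10.3.3.4:

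1. Keep the pill count, but do not count unreturned pills as taken beyond the doses prescribed up to the last dose date. Intake above the prescribed amount that is documented on the CRF should still count.
2. Reconcile the count with the CRF and diary record of missed and vomited doses, and say which source prevails when they disagree.
3. Report compliance and relative dose intensity a second time with vomited doses subtracted, labelled as a lower bound.

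In the Schedules of Activities, reconcile the diary-review line in Tables JZFA.2.1 and JZFA.2.2 with Section 7.6.

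The cost is a few lines of wording, a little more analysis work and slightly less favourable dose-intensity figures. If the reconciliation extends diary review past Cycle 1, it also costs some site time. The dosing deviations are already to be recorded on the CRF under Section 7.6.

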5.1.3. Study Period Definitions

Baseline/Screening: Begins when the informed consent form (ICF) is signed and ends at the first study treatment (defined as receiving any study drug); if no study treatment is given, baseline/screening ends with the decision not to enroll. This period lasts up to 28 days.

Study Period: The overall study period for Study JZFA begins the day of the first patient's first dose of study treatment and ends at overall study completion (as defined in Section [5.3](#)).

- **Study Treatment Period:** Begins with the day of the patient's first study treatment and ends the day the patient and investigator agree that the patient will discontinue study treatment (discontinuation of assigned study drug; Section 8.1). Individual patients who enroll in Study JZFA may continue treatment until they have confirmed progressive disease or discontinue study treatment for any other reason (Section 8).
- **Post Study Treatment Follow-Up Period:** Begins the day the patient and investigator agree that the patient will discontinue study treatment and ends the day of the patient's death, lost to follow-up, or overall study completion, whichever is earlier. It includes one 30-day safety follow-up visit and a long-term follow-up, as follows:
 - **30-Day Safety Follow-Up Visit:** Occurs 30 ± 7 days after the decision is made to discontinue from study treatment.
 - **Long-Term Follow-Up:** Begins the day after 30-day follow-up visit is completed and ends with the patient's death, lost to follow-up, or overall study completion, whichever is earlier.

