7.4. Dose Modification

Doses of the study drugs may need to be delayed, reduced, or discontinued to manage specific AEs or other toxicities. Investigators should review the relationship of an AE to the study drug to determine if study drug requires dose adjustment or delay ([Table JZFA.7.2](#)).

When a study drug is delayed, if possible and appropriate, patients should resume study treatment within 1 treatment cycle and, if not possible, then every effort should be made to start on the first day of the next dosing cycle. In rare circumstances, a delay >28 days may be permitted before permanent treatment discontinuation, as long as the patient has clinical benefit without objective disease progression and is recovering from the toxicity. Such circumstances must be discussed with Lilly. All dose modifications should be documented, including the approach taken, and a clear rationale for the need for modification.

Any patient who requires a dose reduction will continue to receive the reduced dose for the remainder of the study. Any patient who has had 2 dose reductions and who experiences a toxicity that would cause a third dose reduction must be discontinued from study treatment.

If the patient is in Cycle 6 or beyond and is continuing to receive benefit from therapy, additional delays may be acceptable if agreed upon by both the investigator and the Sponsor. If a patient has a non-drug-related AE (for example, pneumonia or prolonged flu) requiring a delay of more than 1 week, the patient may continue on therapy if, in the opinion of the investigator, he/she is showing benefit from therapy and has recovered sufficiently from the AE. Additional procedures may be required for delayed patients before resuming treatment.

Table JZFA.7.2. Dose Modifications in Patients due to Toxicity

Toxicity Type	Toxicity Profile and Severity	Dose Suspension	Dose Reduction
Hematologic toxicity	Grade 3	Dose MUST be suspended until toxicity resolves to at least Grade 2.	Dose MAY be reduced by 1 dose level at the investigator's discretion.
Hematologic toxicity	Recurrent Grade 3	Dose MUST be suspended until toxicity resolves to at least Grade 2.	Dose MUST be reduced by 1 dose level.
Hematologic toxicity	Grade 4	Dose MUST be suspended until toxicity resolves to at least Grade 2.	Dose MUST be reduced by 1 dose level.

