Hematologic toxicity: Patient requires administration of blood cell growth factors	Regardless of severity. Growth factors use according to ASCO guidelines	Dose MUST be suspended for at least 48 hours after the last dose of blood cell growth factors was administered and until toxicity resolves to at least Grade 2.	Dose MUST be reduced by 1 dose level unless already performed for incidence of toxicity that lead to the use of growth factor.
Nonhematologic toxicity (except diarrhea)	Persistent or recurrent Grade 2 that does not resolve with maximal supportive measures within 7 days to baseline or Grade 1	Dose MAY be suspended until toxicity resolves to either baseline or Grade 1.	Dose MAY be reduced by 1 dose level – investigator's discretion.
Nonhematologic toxicity	Grade 3 or 4 that does not resolve with maximal supportive measures within 72 hours to baseline or Grade 1	Dose MUST be suspended until toxicity resolves to either baseline or Grade 1.	Dose MUST be reduced by 1 dose level.
Diarrhea	Requires hospitalization for Grade 3 or 4	Dose MUST be suspended until toxicity resolves to at least Grade 1.	Dose MUST be reduced by 1 dose level.
Diarrhea	Persistent or recurrent Grade 2 that does not resolve with maximal supportive measures within 24 hours to at least Grade 1	Dose MUST be suspended until toxicity resolves to at least Grade 1.	Dose MAY be reduced by 1 dose level – investigator's discretion.
Diarrhea	Persistent or recurrent Grade 1 that does not resolve with maximal supportive measures within 24 hours to baseline	Patient to be followed for 48 hours to ensure grade does not worsen.	Dose MAY be maintained during monitoring – investigator's discretion.
Diarrhea	Diarrhea recurs despite maximal supportive measures after resuming same dose level after initial Grade 2 diarrhea	Dose MUST be suspended until toxicity resolves to at least Grade 1.	Dose MUST be reduced by 1 dose level.
Bloody diarrhea	Any grade	Dose MUST be suspended until bloody diarrhea resolves and diarrhea resolves to at least Grade 1.	Dose MUST be reduced by 1 dose level.
Nonhematologic toxicity (laboratory)	Total bilirubin $>2 \times$ ULN with ALT/AST $>3 \times$ ULN in the absence of cholestasis	Dose MUST be permanently suspended.	Dose MUST be permanently suspended.

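### SAP 6.8.1 ends the dose-intensity divisor at the last dose taken, so a toxicity suspension never followed by re-dosing is left out, while one followed by a single dose counts in full

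*SAP*

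**What the plan says.** SAP 6.8.1 (Extent of Exposure) defines the time base for once-daily dosing: "The duration of therapy for the QD schedule will be calculated as last dose date-first dose date+1". Dose intensity is the total dose taken divided by that duration. Relative dose intensity is 100 times the ratio of actual to planned dose intensity per day. Planned dose intensity is not defined. The only guidance is this remark: "Note that planned dose is the same as actual dose if there is no dose modification or cycle delays".

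The protocol's treatment period ends elsewhere. Under Protocol 5.1.3 it "ends the day the patient and investigator agree that the patient will discontinue study treatment". Between the last dose and that day there can be a suspension. For several toxicities, Table JZFA.7.2 in Protocol 7.4 has entries such as "Dose MUST be suspended until toxicity resolves to either baseline or Grade 1". Section 7.4 aims at resumption within a cycle but foresees longer holds: "In rare circumstances, a delay >28 days may be permitted before permanent treatment discontinuation".

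Protocol 10.3.3.4 requires dose intensity to be summarized for all treated patients.

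**The concern.** A suspension that ends in discontinuation is a path the protocol describes. It lies inside the protocol's treatment period and outside the SAP's divisor. If the patient takes even one more dose, the whole suspension enters the divisor and lowers the result. If the patient never resumes, which is the worse outcome for tolerability, the suspension has no effect. On this feature the measure puts patients in the wrong order.

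What is at stake is how to read the one planned summary of how much of the intended dose was delivered. Treatment compliance cannot take its place, because SAP 6.5 and Protocol 10.3.3.4 compute it after allowing for protocol-defined dose adjustments, which removes toxicity holds by design.

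**Working it through.** The documents give no numerical dose-intensity result, so there is no figure to reproduce. The check applies the SAP formulas to example dosing histories.

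**Inputs**
- Planned schedule: one dose on each day of a 28-day cycle (Protocol 7.2.1).
- SAP divisor: last dose date − first dose date + 1 (SAP 6.8.1).
- Alternative divisor: first dose to the discontinuation decision (Protocol 5.1.3), taking the decision to fall on the last held day.
- Planned dose intensity: the assigned daily dose, not lowered after a reduction (assumption).
- Days dosed and days held: assumptions, chosen to show a range.

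**Step 1. Full dosing, then a final hold.** With full doses, relative dose intensity is 100 × days dosed / divisor days. The SAP divisor equals the days dosed, so the result is always 100%.

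| Days dosed | Days held | SAP | To decision date | Difference (points) |
|---|---|---|---|---|
| 14 | 28 | 14/14 = 100% | 14/42 = 33.3% | 66.7 |
| 28 | 14 | 28/28 = 100% | 28/42 = 66.7% | 33.3 |
| 28 | 28 | 28/28 = 100% | 28/56 = 50.0% | 50.0 |
| 56 | 14 | 56/56 = 100% | 56/70 = 80.0% | 20.0 |
| 84 | 28 | 84/84 = 100% | 84/112 = 75.0% | 25.0 |

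**Step 2. The same hold, with and without one further dose.**
- 10 days dosed, 28 held, 1 dose: 11/39 = 28.2%.
- 10 days dosed, 28 held, no further dose: 10/10 = 100% under the SAP, and 10/38 = 26.3% to the decision date.

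The order is reversed under the SAP and correct under the alternative.

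**Step 3. Patients with earlier modifications.**
- 28 days at 15 mg, 28 days at 8 mg (illustrative doses from Table JZFA.7.1), then 28 held: total 28 × 15 + 28 × 8 = 644 mg. SAP: 644/56/15 = 76.7%. To the decision date: 644/84/15 = 51.1%.
- 10 days dosed, 7 omitted, 11 dosed, then 28 held. SAP: 21/28 = 75.0%. To the decision date: 21/56 = 37.5%.

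**Step 4. Dependence on the undefined term.** Suppose planned dose intensity meant the planned dose of the cycles started, divided by first-to-last-dose days. The 10-day patient would then score 10/28 = 35.7%, but the implied planned daily dose would be 28/10 = 2.8 times the assigned one. Patients dosed for 28 or 56 full days would still score 100%. Dose intensity in mg/day needs no planned value, and it shows the same reversal: 0.28 against 1.0 times the assigned dose in step 2.

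**Step 5. Effect on a dose level's mean.** Overstatement = share of patients affected × individual difference (20 to 66.7 points in step 1), with the other patients unaffected.
- 5% affected: 1.0 to 3.3 points.
- 10% affected: 2.0 to 6.7 points.
- 20% affected: 4.0 to 13.3 points.

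**The case against.** The strongest reply is that little depends on this summary. Protocol 10.3.2 bases the RP2D on DLTs, TEAEs, PK and PD. Escalation uses the N-CRM recommendation, the observed DLT rate and the PK/PD data (Protocol 7.1.1.2). The Phase 1b safety review counts DLT-equivalent toxicities (Protocol 10.3.4, SAP 6.12). Relative dose intensity is named in none of these. Intolerance is also visible elsewhere: in dose adjustments with reasons, duration of therapy and cumulative dose (SAP 6.8.1), in AEs leading to dose adjustment or discontinuation (SAP 6.8.2), and in reasons for discontinuation (SAP 6.3). All of this stands, and it limits the point to a descriptive measure.

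It can also be said that the first-to-last-dose version legitimately measures intensity while dosing, and that Protocol 5.1.3 separates treatment from follow-up without setting an exposure divisor. That stands too. A reader might infer that the SAP contradicts the protocol, but Protocol 10.3.3.4 prescribes no divisor.

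The size rests on assumed hold lengths and frequencies. Section 7.4 calls delays beyond 28 days rare. For the hepatic criterion in Table JZFA.7.2 suspension is permanent at once, so the decision may nearly coincide with the last dose.

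Finally, a decision date may be missing for a patient who dies on treatment or is lost to follow-up, and a longer divisor also picks up delays unrelated to toxicity. The fix has to provide for the first and accept the second.

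None of this removes the reversal in step 2. It follows from the stated formula, and no other section corrects it.

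**Conclusion.** The point holds as a limitation of a descriptive dose-delivery summary that is cheap to correct. The SAP formula leaves out a final toxicity hold and counts the same hold in full once a dose follows it. The effect in one patient can be large (100% against 50% for 28 days dosed and 28 held). The effect on a dose level's mean is about 1 to 13 points if 5% to 20% of patients are affected, with holds as in the examples. The documents give neither the frequency nor the hold lengths.

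Three stronger readings are tempting and are not supported:
- That any patient who stops for toxicity scores 100%. This needs full dosing before the hold and the assumed meaning of planned dose intensity. The examples with earlier modifications give 76.7% and 75.0%, although these too are overstated.
- That the measure would mislead the choice of RP2D. It is not a named input, and it misleads on tolerability only if read apart from the other safety summaries.
- That the overstatement grows with dose. This assumes such holds become more frequent at higher doses, and the documents give no figure for it.

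**What to change.** In SAP 6.8.1:
- Define planned dose intensity per day as the assigned daily dose.
- Compute dose intensity and relative dose intensity over the days from first dose to the date of the decision to discontinue treatment. Use the date of death or last contact where there is no decision date, and the data cut-off for patients still on treatment.
- Report this beside the existing first-to-last-dose version, labelled as intensity while dosing.

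The cost is a short SAP revision and a small programming change. Protocol Section 8 already has the date of discontinuation collected for all patients, and conduct and sample size are untouched. The downside is that the added figure will be somewhat lower and will include short gaps before progression or administrative stops. Showing both versions lets the reader see how much of the difference arises after the last dose.
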